 4 The amount of information was just right
 5
 6
 7 Too much information was provided

How clear was the information on the DCIS website?

1 Not at all clear
 2
 3
 4 Somewhat clear
 5
 6
 7 Extremely clear

How helpful was the information on the DCIS website for making a decision about DCIS treatment?

- 1 Not at all helpful
- 2
- 3
- 4 Somewhat helpful
- 5
- 6
- 7 Extremely helpful

Would you recommend the DCIS website to a friend diagnosed with DCIS?

- 1 No
- 2
- 3
- 4 Not sure
- 5
- 6
- 7 Yes

0% 33% 100%

How likely might a breast biopsy miss invasive cancer?

- A biopsy will always show correctly if there is invasive cancer
- There is about a 1-5 % chance that biopsy misses invasive cancer
- There is about a 6-10 % chance that biopsy misses invasive cancer
- There is about an 11-15 % chance that biopsy misses invasive cancer
- There is a more than 15% chance that biopsy misses invasive cancer

Is DCIS the same as invasive breast cancer?

- Yes
- No

The following options are used to treat DCIS patients (choose all that apply):

- Active monitoring
- Endocrine therapy
- Lumpectomy
- Mastectomy
- Chemotherapy
- Radiation

0% 36% 100%

For a woman diagnosed with DCIS, how much does waiting 3-4 weeks to make a treatment decision affect her chances of survival?

- A lot
- Somewhat
- A little or not at all

With active monitoring, about how many women diagnosed with DCIS do you think will die of breast cancer in 10 years?

- Most will die of breast cancer
- About half will die of breast cancer
- Most will NOT die of breast cancer

After which treatment is it more likely that women will need to have a second surgery to remove leftover tumor cells?

- Lumpectomy
- Mastectomy without reconstruction
- Equally likely for both

Which treatment option does NOT affect the appearance of the breast?

- Active monitoring
- Lumpectomy
- Lumpectomy with radiation
- Mastectomy

On average, which DCIS patients do you think have the highest chance of being diagnosed with invasive cancer in the same breast, within 10 years of diagnosis?

- Women who choose active monitoring
- Women who choose a mastectomy
- Women who choose a lumpectomy with radiation
- There is no difference between the above options

After a lumpectomy, what is the traditional schedule for radiation treatment?

[figure not shown]
- 1 day a week for 5 to 6 weeks
- 3 days a week for 6 weeks
- 5 days a week for 3 weeks
- 5 days a week for up to 10 weeks

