H1: Participants who receive in-depth AM information are more likely to choose AM post-tool compared to participants in the control group.

Secondary Outcome 1: Post-tool acceptability of the different treatment options. Measured as categorical 5-point Likert scale from “Not at all comfortable” (1) to “Very comfortable” (5); analyzed as continuous variable. The following question is repeated four times, each time substituting OPTION X for one of the four treatment options:

- Q2.1: How comfortable would you be with **OPTION X** as your initial treatment for DCIS?

H2.1: Participants who receive in-depth AM information report higher AM acceptability compared to participants in the control group.

Secondary Outcome 2: Subjective perception of active monitoring riskiness. Measured as categorical 5-point Likert scale from “Not at all likely” (1) to “Very likely” (5); analyzed as continuous variable.

Q2.2: If you choose active monitoring as your treatment, how likely is it that your DCIS will progress to invasive cancer within 10 years after diagnosis?

- (1) Not at all likely
- (2)
- (3)
- (4)
- (5) Very likely

H2.2: Participants who receive in-depth AM information perceive AM to be subjectively less risky than participants in the control group.

Secondary Outcome 3: Post-tool mastectomy choice. Presented to participants as a categorical item: active monitoring, lumpectomy, lumpectomy with radiation, mastectomy. Recorded for analysis as binary: mastectomy vs non-mastectomy.

Q2.3: see Q1

H2.3: Participants who receive in-depth AM information are less likely to choose a mastectomy compared to participants in the control group.

Secondary Outcome 4: Change in self-perceived knowledge about DCIS. Measured pre- and post-tool as a categorical 5-point Likert scale from “I know very little about DCIS” (1) to “I know a lot about DCIS” (5); analyzed as continuous variable.

Q2.4: How much do you know about ductal carcinoma in situ, abbreviated as DCIS?

- (1) I know very little about DCIS
- (2)
- (3)
- (4)
- (5) I know a lot about DCIS

H2.4: In both groups, self-perceived knowledge about DCIS is higher post-tool compared to pre-tool.

H. Exploratory Aims

See next sections for details about covariates and additional scales used in the explanatory aims.

Exploratory Aim1: Descriptive analyses of the following scales:

- a) DCIS knowledge (11 questions), including AM knowledge (2 questions)
- b) Choice confidence (1 question)
- c) Information needs satisfaction

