- d) Preparation for decision making
- e) Treatment choice reason

Exploratory Aim 2: Does knowledge about AM mediate AM acceptability?

Exploratory Aim 3: Is the score of the minimizer-maximizer scale associated with post-tool treatment choice?

Exploratory Aim 4: Are extreme scores of the minimizer-maximizer scale (1 or 6) associated with less accurate DCIS knowledge?

Exploratory Aim 5: What covariates and personality scales are associated with post-tool treatment choice and AM acceptability?

Exploratory Aim 6: Does subjective perception of AM riskiness mediate choice of AM?

I. Covariates

1) Age: Will be known before participation begins due to the recruitment method; will be used to ensure equal study arm assignment within the two stratification groups. For the analysis we will use self-reported age (years).

2) Race & Ethnicity: Asked as two separate questions

Are you Hispanic or Latina?

- Yes
- No

With which of the following groups do you most closely identify?

- White (1)
- Black or African American (2)
- American Indian or Alaska Native (3)
- Asian or Pacific Islander (4)
- Other (5)

3) SES: 4-level categorical variable

How would you describe your household's financial situation right now?

- After paying the bills, you still have enough money for special things you want
- You have enough money to pay the bills, but little spare money to buy extra or special things
- You have money to pay the bills, but only because you have cut back on things
- You are having difficulty paying the bills, no matter what you do

4) Education: 6-level categorical variable. May be recoded (e.g., college vs no college)

What is your highest level of education?

- Some high school
- High school
- Bachelor's degree
- Master's degree
- Professional degree (e.g., MD, JD)
- Doctorate degree (e.g., PhD)

5) Marital Status: 6-level categorical variable. May be recoded (e.g., married vs not married)

What is your current marital status?

- In Relationship
- Married
- Divorced
- Separated
- Single
- Other

6) Short Graph literacy. Single score derived from 4 items, each scored as correct or incorrect. Correct answers are summed for a total "graph literacy score" (0-4). See "Survey" document for details.

7) Current Health. Self-reported health status (visual analog scale, 0-100%), see "Survey" document for details.

J. Additional scales (See "Survey" documents for details about each scale)

- Choice confidence (Chambers et al., 2012) (post-tool)

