Finally, we will perform exploratory attrition analyses. First, we will compare the number of participants who expressed interest, consented, started the experiment, finished the experiment, and were included in final analysis. Second, if there are 20 or more participants who started the experiment but did not finish it, we will compare any completed baseline items

K.5. Missing Data

During data checks, we will determine the degree to which variables of interest are going unanswered. Depending on the type of variable and the amount of missingness across all subjects, as well as the balance across study arms, we will consider different imputation methods, or removal of the covariate from the models. For variables with a low degree of missing values (<=5%), we will use simple imputation methods, substituting in the median or modal response. For variables with a higher degree of missing values (>5%) we may perform multiple imputation with 25 imputations.

K.6. Subgroup Analysis

Stratification by age group (<65 vs. \geq 65 years) will occur during study arm assignment to ensure equal age group representation in each study arm. Further, we plan to analyze the effect of study arm on treatment choice separately within each of the two major age groups, while still including age in years as a continuous covariate. If there is a very marked difference in the stratified analysis, we could consider only including the stratified analysis (i.e. if the overall model is a poor indication of treatment effects because of the subgroup differences).

K.7 Sensitivity Analyses

Intent-to-treat vs. per Protocol analysis: Run both Table 1 and primary outcome model for the final sample with all exclusion criteria applied, as well as for the larger sample of all participants who were randomized and completed the post-survey. This comparison will only be necessary if >5% of those randomized, who completed the post-survey, were excluded due to not clicking through the guide and tool (new criteria).

Anticipated tables and figures

Table 1. Participant characteristics (demographic, pre-knowledge), overall and by treatment arm

Table 2. Primary and secondary outcomes at each time point, and change, by treatment arm

Table 3. Intervention effects on primary outcome

Figure 1: Proportion of treatment choice selections post-tool by study arm (*format TBD*)

Table 1. Patient characteristics, overall and by arm (demographics by age group included as a supplemental table)

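### SAP K.5's modal fill can credit a blank knowledge or graph-literacy item as a correct answer: a minor gap, limited to exploratory aims, that a short addition to K.5 would close

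*SAP*

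**What the plan says.** SAP K.5 (Missing Data) covers variables of interest that go unanswered. It first says that, depending on variable type, amount of missingness and balance between arms, "we will consider different imputation methods, or removal of the covariate from the models". It then gives a rule by amount. At low missingness: "For variables with a low degree of missing values (<=5%), we will use simple imputation methods, substituting in the median or modal response". Above that: "For variables with a higher degree of missing values (>5%) we may perform multiple imputation with 25 imputations".

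Two sets of items have right and wrong answers:

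- **DCIS knowledge.** SAP section H, Exploratory Aim 1, lists 11 questions, 2 of them on active monitoring (AM). The items are in Protocol Appendix 1; one asks "With active monitoring, about how many women diagnosed with DCIS do you think will die of breast cancer in 10 years". Aim 2 asks "Does knowledge about AM mediate AM acceptability", and Aim 4 asks whether extreme maximizer-minimizer scores are "associated with less accurate DCIS knowledge".
- **Graph literacy.** SAP section I, covariate 6: "Single score derived from 4 items, each scored as correct or incorrect". The correct answers are then added to give a score from 0 to 4. This is a candidate covariate for Exploratory Aim 5.

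The completion check in SAP section E requires answers on treatment choice, the four acceptability items, perceived riskiness and self-rated DCIS knowledge before and after the tool. It does not name the 11 knowledge items or the 4 graph-literacy items.

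**The concern.** Filling a gap with the most common response is a tolerable shortcut for a demographic item. On a test item the response is the measurement: if the most common answer is correct, the fill records that the woman knew something she did not show she knew. If it is incorrect, the same blank scores zero. Her score then depends on how other women answered.

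The questionnaire adds to this. None of the 11 knowledge items offers a don't-know option, so a blank may be how a woman says so. All four graph-literacy items do offer a can't-say option, which earns no credit; under modal fill with a correct mode, skipping the item would score higher than using that option. That also sits badly with the section I rule that the score is the sum of correct answers.

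At stake is the objective evidence on knowledge. Part (ii) of the main hypothesis concerns knowledge of risk trade-offs. The formal knowledge outcome (Secondary Outcome 4) is self-rated, so the 11 items are the only factual test.

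**Working it through.** **Inputs.** Analysed sample: 101 per arm, 202 in total (SAP section E). Threshold: 5% (K.5). Items: 11 knowledge, 2 of them AM (section H); 4 graph literacy (section I). The documents give no percent-correct figures and no blank rates, so those below are assumptions.

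**The plan's own figure.** K.5 gives only the 5% threshold and 25 imputations. The design figure is 90% power at 5% versus 20% uptake with 101 per arm. By the normal approximation (pooled variance under the null, two-sided 5%):

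- null SE = √(2 × 0.125 × 0.875 / 101) = 0.0465
- alternative SE = √((0.05 × 0.95 + 0.20 × 0.80) / 101) = 0.0453
- z = (0.15 − 1.96 × 0.0465) / 0.0453 ≈ 1.30, so power is 90.3%

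The figure reproduces. It involves treatment choice only, which the completion check requires.

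**Largest number of blanks per item.** 0.05 × 202 = 10.1, so at most 10 women (10/202 = 4.95%).

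**Largest credit when the mode is correct, compared with scoring a blank as not correct.**

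| Score | Calculation | Maximum rise in mean |
|---|---|---|
| One item | 10/202 | 4.95 points |
| DCIS knowledge | 11 × 10/202 | 0.54 of 11 |
| AM knowledge | 2 × 10/202 | 0.10 of 2 |
| Graph literacy | 4 × 10/202 | 0.20 of 4 |

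The scale totals need every item at the 5% limit and every mode correct. Where the mode is wrong, the rise is 0. If blank responders would have answered like the others, with share p correct, the excess credit per item is only 4.95 × (1 − p): 2.5 points at p = 50%, 1.0 at 80%, 0.5 at 90%.

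**Difference between arms.** Assume 85% correct (intervention) and 75% (control) among those who answered, and a correct mode.

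- *All 10 blanks in control.* Blank as not correct: 85.0 − 91 × 0.75/101 = 85.0 − 67.6 = 17.4 points. Complete case: 10.0. Modal fill: 85.0 − (68.25 + 10)/101 = 85.0 − 77.5 = 7.5.
- *7 in control, 3 in intervention.* Blank as not correct: (98 × 0.85 − 94 × 0.75)/101 = 12.7. Modal fill: (83.3 + 3 − 70.5 − 7)/101 = 8.7.
- *5 in each arm.* Blank as not correct: (96 × 0.85 − 96 × 0.75)/101 = 9.5. Modal fill: also 9.5, because both arms gain 5/101.

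The choice of scoring therefore moves the arm difference only when blanks are unbalanced. With all blanks in control, modal fill falls below the complete-case value and not-correct scoring lies above it.

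**The case against.** The strongest reply is that K.5 is not an unqualified rule. Its opening sentence makes the method depend on variable type and arm balance, which are the two features that matter here. K.5 also does not say whether it works on raw responses, scored items or total scores, or whether the mode is pooled. The section I summing rule already suggests that a graph-literacy blank earns nothing, and the SAP sends readers to the survey documents for scale details; Appendix 1 shows the items but no scoring key. In part this stands: modal filling of single test items is one reading, not a certainty. But the opening sentence only promises to consider alternatives, while the low-missingness sentence commits to a method and names no exception.

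A second reply is that scoring blanks as wrong is itself a convention. In the 10/0 example it lies 7.4 points from the complete-case value (17.4 against 10.0), and modal fill only 2.5 (7.5 against 10.0). This also stands. It is why the fix needs a complete-case check alongside.

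Two stronger readings are tempting and are not supported. A reader might infer that the mode is usually the right answer; the documents give no percent-correct figures, and several items have four or five close numerical options on which the commonest answer could be wrong. A reader might also infer that control women, who get no in-depth AM information, will leave more AM items blank, so that the rule hides a knowledge gain. That is plausible, but nothing documents it, nor that a blank means ignorance rather than an accidental skip.

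**Conclusion.** The point holds as a minor improvement. Followed literally, K.5 credits a blank test item as correct whenever the modal response is correct, and no visible text clearly prevents this. The ceilings in the table rest on the plan's own 5% threshold and on 202 analysed women; the effect on the arm difference rests on assumed percent-correct values and splits of blanks, with 10/0 the extreme case.

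The reach is limited to Exploratory Aims 1, 2 and 4 (knowledge) and 5 (graph literacy as a candidate covariate). Aim 1 is descriptive, and K.4 leaves Aims 1 to 4 to ad hoc analysis. It would be wrong to infer that the trial's main results are at risk: the items behind the primary and secondary outcomes cannot be blank among the 202, the primary model contains only arm and age group, and sample size and power do not change.

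**What to change.** Add to K.5:

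> Median and modal imputation do not apply to the 11 DCIS knowledge items or the 4 graph-literacy items. For women who reached the end of the survey, an unanswered item is scored as not correct. Blanks are reported per item and by arm, and each analysis that uses these scores is repeated on complete cases.

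Apply the same scoring above 5% missing, so that the treatment of a blank does not switch at the threshold. Say what counts as unanswered on the two choose-all-that-apply knowledge items. The existing imputation rules can stay for attitude scales and demographics.

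The cost is a few lines of text, one small table and a repeat run of exploratory analyses, with no change to recruitment. The downside is that an accidental skip counts as not knowing, and if blanks are unrelated to knowledge but unbalanced between arms, this scoring can exaggerate an arm difference. The complete-case check and the counts by arm would reveal both.

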- Used Mantel-Haenzel test (note: Table below created with power.prop.test in R)
- Scenario 1: we have 90% power with n=101 in each arm
- Scenario 2: if Δ is still 15% but control/intervention at 10%/25% we still have 80% power
- Scenarios 3-6: if, as estimated in usability testing, uptake of AM is 40%, then for Δ of 15%, 20%, 25% and 30%, we have power of 62%, 88%, 98% and 99%

Scenario	n (per arm)	P1	P2	Δ	Power
1	101	5%	20%	15%	90%
2	101	10%	25%	15%	80%
3	101	10%	40%	30%	99%
4	101	15%	40%	25%	98%
5	101	20%	40%	20%	88%
6	101	25%	40%	15%	62%

Randomization

- We prepare two separate random streams, one for younger (<65 years) and one for older (≥ 65 years) participant strata.
- Each stream is block randomized, with block size $k=6$.
- For each consented participant, we check for survey completion. Survey completion is defined as:
 - Reached the end of the survey (and thus were paid); and
 - Answered the treatment choice question (primary outcome); and
 - Answered the treatment acceptability questions (n=4; secondary outcome); and
 - Answered perceived riskiness question (secondary outcome); and
 - Answered both pre- and post-tool self-reported knowledge questions about DCIS (secondary outcome); and
 - Clicked on the Guide and the Decision Support Tool links provided in the survey.
- We continue to randomize until we reach n=101 participants (per arm) who pass the survey completion check.

F. Study Sample

Potential patients will be identified through Duke electronic health record system Epic and invited through the MyChart patient portal. Duke has an “opt-out” system that allows patients to be contacted directly about research studies for which they may be eligible. If a patient agrees to participate in the study by replying to a MyChart message, the patient will be consented and referred to the survey link.

Inclusion criteria

- Female
- Age 50-79

- No history of DCIS/breast cancer [medical record only]
- Negative mammogram in past 12 months [medical record only]

G. Outcomes & Hypotheses

Primary Outcome: Post-tool choice of active monitoring (AM). Presented to participants as a categorical item: active monitoring, lumpectomy, lumpectomy with radiation, mastectomy. Recorded for analysis as binary: AM vs non-AM.

Q1: If you were a patient diagnosed with DCIS, what treatment option would you choose?

[Order is randomized]

- Active monitoring
- Lumpectomy
- Lumpectomy with radiation
- Mastectomy

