To answer the primary research question, we will use a log-binomial regression model to test the effect of study arm on binary treatment choice (see primary outcome measure), controlling for age group to account for the stratified design:

$$(1) \quad Y_i = \beta_0 + \beta_1 X_i + \beta_2 a_i$$

where

Y_i = subject i 's response: $Y=1$ for AM, $Y=0$ for non-AM choice

X_i = subject i 's study arm: $X=0$ for control arm, $X=1$ for intervention arm

a_i = subject i 's age group: $a=0$ for age <65 years, $a=1$ for age ≥ 65 years

The main effect of interest (1) is represented by β_1 which quantifies the difference in AM uptake between the two arms and will be reported as $\exp(\beta_1)$ with 95% confidence interval [CI].

To follow the CONSORT statement and because the control arm prevalence is expected to be $>10\%$ we will report risk ratios as the relative measure, and absolute risks in both arms.

K.3. Secondary outcome analyses

Secondary Outcome 1. Linear regression model, as in (1), reported as β_1 (95% CI).

Secondary Outcome 2. Linear regression model, as in (1), reported as β_1 (95% CI).

Secondary Outcome 3. Same analysis as primary outcome analysis, reported as β_1 (95% CI).

Secondary Outcome 4. Linear regression model, controlling for age group, and with random intercepts to account for within-subject dependence.

Model:

$$(1) \quad Y_{ij} = \beta_0 + \beta_1 X_i + \beta_2 t_j + \beta_3 t_j X_i + \beta_4 a_i$$

where

Y_{ij} = subject i 's response at time t_j . (0=surgical; 1=AM)

t_j = time (0=pre-tool; 1=post-tool)

X_i = subject i 's study arm (0 = control; 1 = intervention)

a_i = subject i 's age group: $a=0$ for age <65 years, $a=1$ for age ≥ 65 years

If the models for secondary outcomes 1-4 do not meet the required assumptions for linear models, we will explore using median regression and/or dichotomizing the continuous variable (e.g., top quartile=high, remaining values=normal/low).

K.4. Exploratory aims analyses

Ad hoc statistical analyses will be performed for exploratory aims 1-4. For Exploratory Aim 5 (association of covariates and additional scales with choice), we will extend the model (1) to include covariates and additional scales as outlined sections I and J above. The additional model features will first be assessed for multicollinearity, with features removed if necessary. We will do model building to identify a final model, and present both unadjusted and adjusted parameter estimates for the final model (Table 3).

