	Overall	Intervention	Control	p-value
Demographics				
Age (mean, SD)				
Age group				
<65				
≥ 65				
Sex (Female, N (%))				
Age (mean, SD)				
Race/Ethnicity				
African-American / Black				
American Indian or Alaska Native				
Asian or Pacific Islander				
Hispanic				
White				
Marital Status				
In a relationship				
Married				
Divorced				
Separated				
Single				
Other				
Education				
High school or less				
Some college				
College graduate				
Post-graduate degree				
Rural (N, %)				
Cancer History				
Maximizer Minimizer Scale (mean, SD)				
General pre-tool Knowledge (mean, SD)				
Breast Cancer				
DCIS				
Additional Scales (TBD)				

Table 2. Primary and secondary outcomes at each time point, by treatment arm

	Control	Intervention
Primary Outcome		
Treatment Choice (AM, N, %)		
Secondary Outcomes		
AM Acceptability (mean, SD)		
AM Perceived Risk (mean, SD)		
Mastectomy uptake (N, %)		
Change in self-perceived DCIS knowledge (post-pre, mean, SD)		

Table 3. Intervention Effects on primary and secondary outcomes

	Intervention Effect Overall		Intervention effect: <65 years		Intervention effect: ≥65 years	
Primary Outcome	RR (95%CI)	ARR (95% CI)	RR (95%CI)	ARR (95% CI)	RR (95%CI)	ARR (95% CI)
Choose AM at post-tool						
Risk ratio (95% CI)						
Absolute risk (95% CI)						
	Intervention Effect		Intervention effect: <65 years		Intervention effect: ≥65 years	
Secondary Outcomes	β (95% CI)	aβ (95% CI)	β (95% CI)	aβ (95% CI)	β (95% CI)	aβ (95% CI)
AM Acceptability						
AM Risk						

RR, relative risk; ARR, adjusted relative risk. Adjusted models include [covariate list] as covariates

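### SAP K.6 allows the overall primary estimate to be left out in favour of two age-stratum estimates after the results are seen, with no defined trigger and no interaction estimate

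*SAP*

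**What the plan says.** K.2 sets the primary analysis: "we will use a log-binomial regression model to test the effect of study arm on binary treatment choice", with age group as the only covariate. Model (1) has main effects for arm and age group. Its result is one overall risk ratio, exp(β1), with a 95% CI.

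Section E sizes the trial for this whole-trial comparison: "Scenario 1: we have 90% power with n=101 in each arm" at 5% vs 20%, and at "control/intervention at 10%/25% we still have 80% power". It gives no stratum sizes. Recruitment stops at 101 completers per arm, with no quota by age.

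K.6 plans separate analyses in women under 65 and women 65 or older. It continues: "If there is a very marked difference in the stratified analysis, we could consider only including the stratified analysis". The reason given is "if the overall model is a poor indication of treatment effects because of the subgroup differences".

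The Table 3 shell places "Intervention Effect Overall" beside the two age columns, so the default is to show all three. Table 2 ("Treatment Choice (AM, N" and %) and Figure 1 ("Proportion of treatment choice selections post-tool by study arm") keep crude choice by arm for the whole trial.

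**The concern.** The K.6 decision is taken once the stratum results are known. The SAP does not say how large a difference must be, on which scale it is judged, or whether a test is involved. The stated reason explains why one might switch, not when. No arm-by-age-group term appears in model (1), K.6 or Table 3; the only product term in the SAP is time by arm, for Secondary Outcome 4. The team would therefore have no planned estimate of whether the strata differ beyond chance.

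What could be lost is the model-based primary estimate with its CI and test. In its place would stand two estimates for which the trial was not sized. Small strata with low control uptake can look very different when the true effect is the same, and a general effect of the tool could then be reported as one confined to younger or older women.

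**Working it through.** **Inputs.** From section E: 101 per arm, α = 0.05 (taken as two-sided, which reproduces the power table), uptake 5% vs 20% or 10% vs 25%. Assumed, because the SAP gives none: stratum splits per arm of 51/50 or 60/41 (50 is used for the power formula), and every reading of a marked difference below.

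**1. The plan's own power.** With p̄ = (p0+p1)/2,

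power = Φ{[|p1−p0|·√n − 1.96·√(2p̄(1−p̄))] / √(p0(1−p0)+p1(1−p1))}.

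- 5% vs 20%, n = 101: (0.15×10.050 − 1.96×0.4677)/0.4555 = 1.297, power 90.3% (SAP: 90%).
- 10% vs 25%, n = 101: (0.15×10.050 − 1.96×0.5374)/0.5268 = 0.862, power 80.6% (SAP: 80%).

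**2. Power in one stratum, same formula.**

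| n per arm | 5% vs 20% | 10% vs 25% |
|---|---|---|
| 60 | 70.5% | 58.2% |
| 50 | 62.4% | 50.6% |
| 41 | 53.8% | 43.0% |

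**3. Chance differences when the true effect is the same in both strata.** There were 400,000 simulated trials per setting. Each stratum was tested with a pooled two-proportion z test, two-sided 0.05. The overall test was Mantel-Haenszel stratified by age group (the test named in section E, standing in for the log-binomial model). Risk ratios had 0.5 added to each count. Ranges cover the two splits.

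| | 5% vs 20% | 10% vs 25% |
|---|---|---|
| Stratum risk ratios differ at least twofold | about 45% | 31-32% |
| Exactly one stratum significant | 45-46% | 50-51% |
| Overall test significant | 92% | 82% |

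The noise comes from small counts: at 5% uptake, 50 control women yield 50×0.05 = 2.5 expected AM choices.

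**4. A formal trigger is much quieter.** Suppose the switch needed a Wald test of the difference in log risk ratios. With equal true effects, p<0.05 would fire in 1.1-1.2% (5% vs 20%) or 2.9-3.0% (10% vs 25%) of trials, and p<0.01 in at most about 0.2%.

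**5. Type I error.** Assume the formal trigger of step 4, and that after a switch any significant stratum counts as the finding. With null uptake from 5% to 25%, the error is 4.4-5.6% (p<0.01) or 5.2-7.8% (p<0.05), against 4.4-5.2% for the overall test.

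**6. Precision of a ratio of risk ratios.** Per stratum, var(log RR) ≈ (1−p0)/(n·p0) + (1−p1)/(n·p1). Taking n = 50 per arm in both strata:

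- 5% vs 20%: 0.95/2.5 + 0.80/10 = 0.46; two strata 0.92; 1.96×√0.92 = 1.88; exp(1.88) ≈ 6.6.
- 10% vs 25%: 0.90/5 + 0.75/12.5 = 0.24; two strata 0.48; 1.96×√0.48 = 1.36; exp(1.36) ≈ 3.9.

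The 95% CI would run from the estimate divided by that factor to the estimate multiplied by it. The approximation is rough at 5% uptake: the chance that 50 control women include no AM choice is 0.95^50 = 7.7%.

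**The case against.** The best defence is that K.6 is tentative, that age is the trial's only stratification factor rather than a subgroup picked afterwards, and that an overall estimate can mislead when effects truly differ between strata. K.2 says without condition that exp(β1) will be reported, and Table 3 has a column for it. Table 2 retains the overall counts, from which a reader could compute a crude risk ratio, CI and test; with randomization stratified by age, these should lie close to the adjusted result. All of this is true and limits the harm. It does not close the gap: K.6 still permits the planned column to be omitted, leaves K.2 and K.6 unreconciled, and crude counts are not the planned model estimate.

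A reader might also infer three stronger things. The first is that the false-positive rate roughly doubles, since two independent tests at 0.05 give 1 − 0.95² = 9.75%. The SAP has no rule that a significant stratum counts as success, and with a formal trigger the inflation is small (step 5). The second is that a positive result would be hidden. When the p<0.05 log-risk-ratio trigger fires under the planned effects, at least one stratum is significant in about 99% of trials, so an effect would still be seen; the risk lies in its age-specific label. The third is that a chance switch is frequent. Under a strict formal trigger it is rare. The twofold and one-stratum figures in step 3 illustrate an informal look, which the SAP does not exclude but does not prescribe either.

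**Conclusion.** The concern holds as a gap in pre-specification. Whether the overall primary estimate is presented can depend on the stratum results, judged by an undefined criterion and without a planned interaction estimate. Its size depends on how the K.6 wording is applied: an informal comparison of stratum risk ratios would often look striking by chance, while a strict test on the K.2 scale would seldom fire. The documents do not show that the sponsor intends to drop the overall result, or that error control is seriously damaged. The stratum splits, the triggers and the any-significant-stratum rule are all assumptions; the wording of K.6 and the sizing for the overall comparison alone are not. It should be corrected before the analysis, because correction costs little and removes a results-driven choice of primary result.

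**What to change.** Replace the K.6 sentence on including only the stratified analysis with:

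*The overall age-adjusted risk ratio from model (1) is always reported as the primary result. The two age-stratum effects are supportive and do not replace it, whatever their size. They are shown with one arm-by-age-group interaction estimate (ratio of risk ratios, the K.2 scale) and its 95% CI, which is descriptive.*

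Add that estimate to Table 3. A risk-difference interaction may be shown as a supplement, but it should not stand alone, because it can show heterogeneity when the risk ratios are equal and control uptake differs by age. State in advance what is reported if a stratum has no AM choices in the control arm.

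The cost is SAP wording and one extra estimate, with no further participants or data. The option to present the strata alone is lost. The interaction estimate will be too imprecise to settle whether the effect differs by age, but a large age difference would still be visible beside the overall result.
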